6.10.2 Imputation Rules for Incomplete Dates

In case of missing partial start and stop dates for concomitant medications, the following rules will be used:

If the start date is missing or partial:

- if the month is missing, use January
- if the day is missing, use the first day of the month under consideration
- if the year is missing, use year of the informed consent date
- if the entire date is missing then:
 - a) If the concomitant medication did not start more than 28 days prior to treatment administration (operation day), use the informed consent date.
 - b) Otherwise, use the 29th day prior to treatment administration.

If the stop date is missing or partial and the concomitant medication is not ongoing then:

- if the month is missing, use December
- if the day is missing, use the last day of the month under consideration
- if the year or the entire date is missing, set the stop date to December 31st, 2099

If the imputed start date is after the stop date, then the imputed start date will be 1 day prior to the stop date.

For AEs, a missing or incomplete onset date will be imputed according to the following conventions.

If only the year is known for the AE onset date, the imputed onset date will be the latest of the following non-missing dates:

- Date of first dose of study drug
- January 1 of the year of AE onset date

If only the month and year is known for the onset date, set the surrogate onset date to the first day of that month and then apply the following rules.

- If the month and year of the onset date is prior to the month and year of the first dose of study drug, then the surrogate onset date will be the imputed onset date.
- If the month and year of the onset date is on or after the month and year of the first dose of study drug, then the imputed onset date will be the latest of the following non-missing dates:
 - Date of first dose of study drug
 - Surrogate onset date

If the imputed onset date is after the adverse event end date, the imputed onset date will be the same as the adverse event end date.

7 **REVISION AND RATIONALE**

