7.3.1 Time Period for Collecting Adverse Event and Serious Adverse Event Information

In order to identify any events that may be associated with study procedures and could lead to a change in the conduct of the study, Astellas collects AEs even if the subject has not received IP. AE collection begins after the signing of the ICF and will be collected through to the last clinical study protocol-defined assessment or when the subject is determined to be a screen failure.

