5.4.1 Adverse Event

AE will be assessed by evaluation of the following variables:

- Treatment-emergent adverse events (TEAEs; frequency, severity, seriousness, and relationship to study drug)
 - TEAE is defined as an AE observed after ASP5354 administration and up to the follow-up period (up to Day 10).
 - If the AE occurs on Day 1 and the onset check box is marked "Onset after first study drug taken" or the both onset check boxes "Onset before first study drug taken" and "Onset after first study drug taken" are marked or left blank, then the AE will be considered treatment emergent.
 - If the AE occurs on Day 1 and the onset check box is marked "Onset before first study drug taken", then the AE will not be considered treatment emergent.
 - If a subject experiences an event both during the pre-investigational period and during the investigational period, the event will be considered as TEAE only if it is reported with a new start date (i.e., as a new AE).
 - Any AEs with onset dates completely missing will be considered TEAEs in summaries unless the investigator has noted on the CRF the event began prior to treatment. AEs with partially missing onset dates will be assumed TEAEs unless the available portion of the date indicates that the onset was strictly before start of study medication.
 - A drug-related TEAE is defined as any TEAE with possible relationship to study treatment as assessed by the investigator or with missing assessment of the causal relationship.

• Serious adverse events (SAEs) include adverse events that are flagged as serious by the investigator on eCRF, or upgraded by the Sponsor based on review of the Sponsor's list of Always Serious terms.

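### The year-only rule for adverse-event onset moves a known prior-year onset to the dose date and can make it treatment-emergent; the SAP does not say which rule decides

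*SAP*

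**What the plan says.** **SAP 6.10.2, year-only onset.** The rule reads: "If only the year is known for the AE onset date, the imputed onset date will be the latest of the following non-missing dates". One candidate is the dosing date; the other is "January 1 of the year of AE onset date". There is no branch for an onset year before the dosing year.

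**SAP 6.10.2, month and year known.** The surrogate date is the first of the month. This rule does have a pre-dose branch, with the condition "If the month and year of the onset date is prior to the month and year of the first dose of study drug". When it is met, the surrogate is kept and the onset stays before dosing.

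**SAP 6.10.2, end-date cap.** The rule reads, in part: "If the imputed onset date is after the adverse event end date, the imputed onset date will be the same as the adverse event end". In other words, an imputed onset cannot fall later than the recorded end of the event.

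**SAP 5.4.1, TEAE status of partial dates.** The clause reads, in part: "AEs with partially missing onset dates will be assumed TEAEs unless the available portion of the date indicates that the onset was strictly before". The comparison point is dosing with ASP5354.

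**SAP 5.4.1, Day 1 check box.** A Day 1 event ticked as starting before study drug is not treatment-emergent. One ticked as after, with both boxes ticked, or with both blank, is.

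**Protocol 7.3.1.** "AE collection begins after the signing of the ICF", so events that start before dosing are recorded.

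**The concern.** The year-only rule discards the one piece of date information the site supplied. A record that says 2020, in a subject dosed in 2021, leaves the imputation with an onset in 2021. The same event recorded more precisely, as December 2020, stays before dosing. Two rules in one section thus treat the same event differently, and the less precise record gets the later date.

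The consequence that matters is TEAE status. The SAP describes no other summary that depends on AE onset dates. Once the event sits on Day 1, the check-box rule can count it as treatment-emergent, while the partial-date clause in the same SAP section says it is not. Two programmers following the SAP could flag it differently. Safety is a secondary objective, and the TEAE tables by system organ class and preferred term (SAP 6.5.1) are a main safety output.

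**Working it through.** The plan gives no figure to reproduce. The check applies the rules as written to an example and then asks how often the condition can arise.

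**Inputs.** The date rules are from SAP 6.10.2 and the TEAE rules from SAP 5.4.1. Screening is Day -28 to -1 (Protocol Table 1). The planned period is about 1Q2020 to 4Q2021 (Protocol synopsis). Dose-level sizes are 3 at the first review and at most 15 (SAP 2.2). The dose date of 12 January 2021 is an illustrative assumption.

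**Step 1: imputed date.** Year-only onset = max(first-dose date, 1 January of onset year). For onset year 2020: max(12 Jan 2021, 1 Jan 2020) = 12 Jan 2021, which is Day 1. Whenever the onset year is before the dosing year, 1 January of that year precedes the dose date, so the maximum is always the dose date.

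**Step 2: sibling rule.** The same event recorded as December 2020 has surrogate date 1 Dec 2020. That month is before the dose month, so the imputed onset is 1 Dec 2020.

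**Step 3: TEAE status for onset year 2020, dose 12 Jan 2021.**

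| AE end date | Day 1 check box | Imputed onset | TEAE by imputed date and box | TEAE by 5.4.1 partial-date clause |
|---|---|---|---|---|
| none, or 15 Jan 2021 | blank or after | 12 Jan 2021 | yes | no |
| none, or 15 Jan 2021 | before | 12 Jan 2021 | no | no |
| 5 Jan 2021 | any | 5 Jan 2021 (capped) | no | no |
| 30 Dec 2020 | any | 30 Dec 2020 (capped) | no | no |

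Both boxes marked behaves like blank. The two routes disagree only in the first row: an event not known to have ended before dosing and not ticked as before. SAP 6.10 mentions imputing AE stop dates, but 6.10.2 gives no rule for them, so a missing end date does not trigger the cap.

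**Step 4: reach.** Collection starts at consent and screening starts at Day -28, so a prior-year onset needs a dose date from 1 to 28 January. In the planned period this is 1 to 28 January 2021, or 28 dose dates.

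**Step 5: size.** One misclassified subject moves a preferred-term row by 1/3 = 33.3 points at n=3, or 1/15 = 6.7 points at n=15. The row does not move if that subject already has the same term as a TEAE. The any-TEAE row moves by this amount only if the subject has no other TEAE.

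**Step 6: with the branch added.** Onset year 2020, dose 12 Jan 2021: imputed onset 1 Jan 2020, not a TEAE, in agreement with SAP 5.4.1.

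**The case against.** The strongest reply is that SAP 6.10.2 only fills in a calendar date and never mentions treatment emergence. SAP 5.4.1 defines TEAE status and tests the part of the date that was collected. Read together, 5.4.1 sets the flag and 6.10.2 sets the date, and there is no conflict. A reader might infer that the SAP necessarily turns a prior-year event into a TEAE. The documents do not support that: no AE code is given, nothing shows which rule is programmed, and a box ticked as before dosing or an end date before dosing keeps the event out.

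That limits the claim but does not remove it. The SAP does not say that the partial-date clause overrides the imputed date. The check-box rule in the same section makes a Day 1 event with blank or doubly marked boxes a TEAE. Even if 5.4.1 does govern the flag, the imputed date still contradicts the recorded year.

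The objection on reach stands in full. The event must start after consent, have both month and day unknown, and precede a January dose. Protocol 10.1 expects data entry within 5 days of the visit, with monitor verification against source. The current protocol version is dated 21 July 2021, and SAP v4.0 incorporates its Amendment 2. If enrolment kept to plan, the only exposed window had already passed, so the correction matters only if such a record exists. Nothing in the documents shows that one does.

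**Conclusion.** Wrong as written, minor. The year-only rule gives a date that contradicts the collected year and the sibling rule. It can give a TEAE flag that SAP 5.4.1 would refuse, and the order of precedence is not stated.

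The 33-point (n=3) or 7-point (n=15) shift applies to the event's own preferred-term row and is an upper figure. A reader might take it as a shift in the overall TEAE rate, but that needs a subject with no other TEAE. A reader might also suspect an effect on dose selection. The committee criteria named in SAP 2.2 are visualization and fluorescence intensity, neither of which uses AE dates, although that list is not exhaustive. The primary endpoint is unaffected, and SAP 6.5 plans no safety hypothesis test.

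The conclusion rests on the planned study dates, on AE collection starting at consent within the 28-day screening window, and on a record with only the year of onset.

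**What to change.** 1. Add to the year-only rule in SAP 6.10.2 the check that the month-and-year rule already has: *if the onset year is before the year of first dose, the imputed onset date is January 1 of the onset year*. Keep the present rule for an onset year equal to or later than the dosing year. No consent-date refinement is needed; the month-and-year rule has none.
2. State that the SAP 5.4.1 clause on the available part of the date governs TEAE status, so an event it excludes stays excluded whatever date is imputed. Word this as protecting the exclusion only. For a year-only onset of 2021, an end date of 5 January 2021 and a dose on 12 January 2021, the clause alone would presume a TEAE, although the end-date cap places the event before dosing.

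The cost is two sentences in the SAP and about one line of code. A listing of AEs with year-only onset dates would show whether any record is affected. Trial conduct does not change.
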